The study PI will ensure the validity of the data system by examining electronic summary case report forms within the data system to ensure adequacy and accuracy of data collection as well as transcription to the database itself after enrollment of the first 5 participants. Agreement will be reviewed and discrepancies will be discussed

Safety Monitoring

The proposed trial will be monitored for safety using both automated and electronic means, as well as by human oversight. The study data system will allow real-time monitoring of study participant distress levels, alerting study staff immediately with any participant report of suicidal ideation. Human safeguards will include the study team, led by the experienced PIs, the Duke Institutional Review Board, and the study Data Safety Monitoring Board (DSMB), as applicable per reporting criteria.

Frequency of monitoring, including plans for interim analysis and stopping rules

The proposed trial will be monitored extensively. In real-time, all study staff will be made aware of any study participant who reports any suicidal ideation. Routine reports on enrollment, adherence, dropout, and study progress will be generated by the study data system and then reviewed by the study team. All primary outcomes will be reviewed as well in a summary view (for the PI; group-based data will not be included) and a group-based view (for the DSMB; treatment group name will be removed). The study DSMB will view data every 6 months.

Safety Review Plan

Study progress and safety will be reviewed monthly (and more frequently if needed). Progress reports, including patient recruitment, retention/attrition, and AEs will be provided to the Independent Monitor(s) semi-annually. An Annual Report will be compiled and will include a list and summary of AEs. In addition, the Annual Report will address (1) whether AE rates are consistent with pre-study assumptions; (2) reason for dropouts from the study; (3) whether all participants met entry criteria; (4) whether continuation of the study is justified on the basis that additional data are needed to accomplish the stated aims of the study; and (5) conditions whereby the study might be terminated prematurely. The Annual Report will be sent to the Independent Monitors and will be forwarded to the IRB and NIA. The IRB and other applicable recipients will review progress of this study on an annual basis.

Protocol Version: 5.1 Dated: 13 June 2022 Page 25 of 42

Study Report Outline for the Independent Monitors(s) (Interim or Annual Reports)

The study team will generate Study Reports for the Independent Monitor and will provide information on the following study parameters: NEST, PHQ-9, GAD-7, and PTSS scores; enrollment success; rate of consent; rate of successful randomization; retention rates; and AE/SAEs. Study Report tables will be generated only from aggregate (not by group assignment) baseline and aggregate safety data for the study population.

Submission of On-Site Monitoring/Audit and Inspection Reports

The IRB, IMC, and NIA Program Officials will receive copies of all study monitoring/audit or inspection reports within 14 day of PI receipt.

Table A

Data type	Frequency of review	Reviewer
Subject accrual (including compliance with protocol enrollment criteria)	Monthly	PI, Internal QA Reviewer
	Semi-annually	Independent Monitor(s)
Status of all enrolled subjects, as of	Monthly	PI, Internal QA Reviewer
date of reporting	Semi-annually	Independent Monitor(s)
Data entry quality control checks on 5% of charts	Weekly	QA Reviewer
Adherence data regarding study visits	Monthly	Pls, Internal QA Reviewer
and intervention	Semi-annually	Independent Monitor(s)
AEs and rates (including out-of-range	Monthly	Pls, Internal QA Reviewer
lab values)	Semi-annually	Independent Monitor(s)
	Annually	NIA FDA (If Applicable)
SAEs (unexpected and related)	Per occurrence	Pls, Independent Monitor (s) NIA, FDA (if applicable)
SAEs (expected or unrelated)	Per Occurrence	Pls, Internal QA Reviewer
	Annually	Independent Monitor (s), NIH/NIA
Unanticipated Problems	Monthly	Pls, Internal QA Reviewer
	Per Policy	IRB, FDA (if applicable)

Data management plan

All study data will be entered by participants and delegated study team members via the PCplanner app and the REDCap data system, as applicable. Participant data entry will primarily utilize our tested, highly secure ePRO system linked to the web application. The study team will abstract relevant clinical data from the EMR and input into the secure REDCap. The PCplanner mobile app backend will reside on a Duke University RHEL Server fronted by a ProxyPass pass through server within Apache HTTPD. The central REDCap database will run on a mirrored Duke University server system with automatic fail-over features and transaction logs. Data will be backed up hourly on the Duke University server and archived four times daily on a mirror server managed by Duke Health Technology System (DHTS). The app and data system will be built to security standards set by both the Duke Information Technology Security Office (ITSO) as well as DHTS; our programmatic partners, Duke ORI, have experience using this paradigm. These standards enforce strict scheduled security patching of all digital resources. Weekly summative (i.e., not group-based) reports will be generated and reviewed by the study team to

Protocol Version: 5.1 Dated: 13 June 2022 Page **26** of **42**

monitor enrollment and retention, safety indices, and missing data.

Study Report Outline for the Independent Monitors(s) (Interim or Annual Reports)

The study team will generate Study Reports for the DSMB and will provide information on the following study parameters: NEST, PHQ-9, GAD-7, and PTSS scores; enrollment success; rate of consent; rate of successful randomization; retention rates; and AE/SAEs. Study Report tables will be generated for baseline and aggregate safety data for the study population.

Data handling and Record Keeping

The study team is responsible for ensuring the accuracy, completeness, legibility, and timeliness of the data reported. All source documents should be completed in a neat, legible manner to ensure accurate interpretation of data. The study team will maintain adequate case histories of study subjects, including accurate case report forms (CRFs), and source documentation. The principal investigator will maintain overall oversight and responsibility of these activities.

Personal identifiers, such as name, date of birth, MRN, diagnoses, dates of admission and discharge, and other relevant clinical information for both patients, family members and the clinicians may be stored in the REDCap study data system. Data will be backed up hourly on the server and archived four times daily on a mirror server managed by the Duke Health Technology Solutions team.

13. Data management

All study data will be input by participants and CRCs via the PCplanner app (noting that the usual control group will do the same via the private study webpage, directly linked to the study RedCAP data system, without access to the PCplanner content). Participant data entry will primarily utilize our tested, highly secure ePRO system linked to our data system. The PCplanner mobile app Ansible backend and the RedCAP study data system will reside on a Duke University RHEL Server fronted by a ProxyPass pass through server within Apache HTTPD. The central RedCAP database will run on a mirrored Duke University server system with automatic fail-over features and transaction logs. Data will be backed up hourly on the Duke University server and archived four times daily on a mirror server managed by Duke Health Technology System (DHTS), a technical partner in this R01 project. The app and data system will be built to security standards set by both the Duke Information Technology Security Office (ITSO) as well as DHTS; our programmatic partners, Duke ORI, have experience using this paradigm. These standards enforce strict scheduled security patching of all digital resources. Routine summative (i.e., not group-based) reports will be generated and reviewed by the study team to monitor enrollment and retention, safety indices, and missing data.

14. Privacy, Data Storage & Confidentiality

Privacy

We believe that risks to privacy associated with study participation will be low based on the steps we plan to take closely safeguard participant privacy, protected health information (PHI; see also next section), and personal information. Study ID numbers, generated randomly at the time of enrollment, and are linked in a separate RedCAP subsystem patient names and medical record numbers. Further, names, birthdates, telephone numbers, addresses, and medical record numbers are only viewable by the study team after entry of a unique username/password combination changed every 3 months. The master list of study ID linkage to this personal data will be deleted after study completion. The RedCAP system stores all data on a secure Duke University server with a sophisticated dual backup system. No PHI is visible in any ePRO user interface (with the exception of the clinician user interface, which will show room number and patient last name—the minimal PHI that would still allow recognition). Study participants cannot view data via the ePRO system, only enter data (a 'one-way view'). Participants access this one-way view ePRO system via secure, PHI-free email or text links sent from our study RedCAP data system.

Protocol Version: 5.1 Dated: 13 June 2022 Page **27** of **42**

Should participant privacy be compromised despite our attention to Duke Information Technology Security Office (ITSO) protocols, we will quickly assess the data exposed, disclose this immediately to all affected participants, and offer the assistance of the Duke ITSO in managing the breach. The *impact* of a privacy breach is difficult to quantify, though could be distressing (phone number, address). For this reason, the study team will make every effort to first prevent such a breach first and foremost.

Confidentiality

Subjects will not be identified on any study reports. University firewalls, multiple passwords, and encryption programs protect the security of the electronic data entry system, which will be housed on a highly secure Duke University server. All personal computers are located in lockable offices and are accessible only by frequently changed passwords. The server room is accessible only to designated University Systems Administrators.

Protected Health Information (PHI)

Duke University endeavors to build technological solutions that preserve the privacy, confidentiality, and security of protected health information (PHI) that may be part of health records or research datasets. PHI is handled according to appropriate Health Insurance Portability and Accountability Act of 1996 (HIPAA) Privacy and Security Regulations. Duke programmers and Duke Research staff who work with sensitive data are required to complete appropriate HIPAA training with periodic updates, complete human subjects and data privacy training, comply with site IT Security Policies, and agree to the provisions of the university Rules of Behavior and Sanction Policy. Duke strives to implement reasonable security controls in its product builds guided by the Federal Information Security Management Act (FISMA), HIPAA, and Appendix III of the OMB Circular A-130.

Of the 18 PHI elements, the study will collect the following at minimum: name (identification), address (to send surveys and/or remuneration), date of birth (to calculate age), telephone number and email address (to contact with surveys), social security number (collected only from those who wish to receive remuneration, as per Duke policy regarding payment reporting to Federal agencies), medical record number of patient (identification), and use of unique PCplanner web URLs through which data are collected in our ePRO system (per Duke / DHTS / ITSO security policy). The study team will enter some of these data into our study data system, while family caregivers will enter others. The PHI collected from clinicians includes, but may not be limited to, their name, area of medical focus, age, and relevant sociodemographic information. No PHI is ever visible in any app user interface seen by family caregivers. The PHI displayed in the PCplanner app includes the patient's last name, bed number, MRN, date of admission, and palliative care trigger(s).

Digital security

The study digital infrastructure consists of a mobile web app browser with an integrated electronic patient reported outcomes (ePRO) function designed by One Cow Standing, LLC (Durham, NC), a research system 'backend' which interfaces with the EMR, and a REDCap study data system. The security features are in line and supported by Duke's Information Technology Security Office (ITSO), the Duke Health Technology Solutions (DHTS) frameworks, HIPAA, and Duke IRB standards. Per DHTS standards, security updates and patches for the PCplanner web app will be required on a weekly basis. Our digital systems are also protected up by the Duke University firewall system and monitored 24 hours a day by DHTS digital security technicians.

Private study website

Study staff and participants will access the online elements through separate secure pathways hosted, monitored, and maintained by Duke University under the general domain of PCplanner.duke.edu.

Protocol Version: 5.1 Dated: 13 June 2022 Page 28 of 42

Study staff will use their University credentials to login in a process identical in security strength to EHR login (i.e., Shibboleth multi-factor authentication). The complete PCplanner system, after development by the Duke Office of Research Informatics (ORI) team and the study team, will be hosted within the secure Duke University Internal Digital Environment and will be composed of an app subserver (app interface, content, ePRO system), the study REDCap database, and system files (e.g., scripts, code, HTML, images).

PCplanner Mobile Web Application

The study team opted for a mobile web application versus a native app such as one downloads from an app store because of its enhanced security. Web applications always have the most recent version, allowing security patches to be pushed out at any time. In contrast, native apps require the user to update their app periodically—a process that many users simply do not do regularly, making the app more vulnerable to security breaches. The programming service providers, One Cow Standing, endeavor to build technological solutions that preserve the privacy, confidentiality, and security of protected health information that may be part of health records or research datasets. Protected Health Information (PHI) is handled according to appropriate Health Insurance Portability and Accountability Act of 1996 (HIPAA) Privacy and Security Regulations. All staff who work with sensitive data are required to complete appropriate HIPAA training with periodic updates, complete human subjects and data privacy training, comply with site IT Security Policies, and agree to the provisions of the University Rules of Behavior and Sanction Policy. Duke, and by extension Duke ORI, strives to implement reasonable security controls in its product builds guided by FISMA, HIPAA, and OMB Circular A-130, Appendix III.

Data security is of the upmost importance for the study, particularly in providing a digital, online intervention for the participants. Beyond the robust security that REDCap provides, One Cow Standing developers have implemented and maintains several security protocols and controls for apps as well. Duke ORI has developed a formal information security program, with a named individual responsible for its overall execution. Duke ORI also periodically conducts an information technology (IT) security risk assessment on its projects, maintains formal documented protocols for reporting security breaches, assesses and manages security risks associated with vendors and subcontractors, maintains employee on-boarding and off-boarding policies that protect study data and integrity, and ensures continuing employee awareness of and education on security policies, standards, and procedures. In terms of development approaches to security, Duke ORI evaluates and installs security patches in a timely fashion (generally weekly per DHTS guidelines), protects systems against self-propagating malware, maintains secure coding policies and practices, and utilizes standardized secure build processes to protect Duke hardware that accesses customer networks, protecting confidential data against attack. Duke does not use of off-shore service providers and/or data center facilities. For our study, the web application and supporting backend system that Duke ORI develops will be hosted internally on a Duke University server behind two secure firewalls. Thus, study data will be stored only on approved, secure University servers. In fact, all development will be conducted at all times on a Duke University server under the strict monitoring of Duke ITSO and DHTS.

REDCap

REDCap, via Duke University's secured platform, will serve as a central database for clinically relevant extracted data from each participant's electronic medical record, as well as serve as an electronic source of secure storage for documentation of study visit completion, protocol deviations or unanticipated problems, adverse and serious adverse events, screening and enrollment logs, as well as the electronic informed consent. Only delegated study team members, such as the investigator(s), statisticians, and study team members will have access to the REDCap.

Protocol Version: 5.1 Dated: 13 June 2022 Page 29 of 42

For data validation, a series of project-defined data checks and conditional constraints can be required to ensure the highest quality data collection. All system login procedures and data submissions will be transported and encrypted via the Transport Layer Security (TLS) protocol to the secure central database at Duke University. The study team will have login/password (reset every 3 months) credentialing for authentication of all study staff. A University-approved plugin will be used to operationalize user-level permissions based on user roles to limit study staff access to authorized records and data fields alone.

The central REDCap database will run on a mirrored Duke University server system with automatic fail-over features, daily backups, and transaction logs. This system is physically located in a Tier II Data Center providing backup power sources, climate control, fire protection, and 24x7 surveillance. Audit logs will be reviewed routinely by Duke Health Technology Solutions staff to verify that security measures are operational. The servers are scanned twice weekly for vulnerabilities and are currently maintained at the highest level of vendor and CERT security recommendations. Data will never be shared outside the project unless authorized by the PIs (and approved by the NIH and IRB). User authentication is based on user passwords as described earlier. Password creation requirements are in place to guarantee "strong passwords" as defined by the CERT security recommendations.

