Protocol Version: 5.1 Dated: 13 June 2022 Page 5 of 42

Clinical Protocol Synopsis

1. Title

PCplanner: operationalizing needs-focused palliative care for older adults in intensive care units

2. Background

The number of older adults who receive life support in an ICU (currently 2 million per year) is increasing while survival remains unchanged. Yet the quality of ICU-based palliative care is highly variable across clinicians and hospitals. Namely, older adults often suffer from untreated symptoms in a technology-focused setting; many caregivers (i.e., family members) report poor quality communication and decision making, and clinicians struggle to connect with each other in a shiftwork environment. Additionally, there are process barriers to improving the delivery of high quality palliative care which include difficulties in efficiently identifying older adult patients and family caregivers with the greatest burden of unmet palliative care needs, engaging family decision makers, and coordinating care by ICU teams and palliative care specialists.

To address these barriers, a mobile app platform prototype called PCplanner (Palliative Care planner) has been developed for patients, their family members, and clinicians. PCplanner directly captures EHR data to automate the identification of older adults with palliative care needs based on clinical characteristics such as dementia and declining health status. The app engages families as partners in their loved one's care by facilitating in a self-report of actual needs. Additionally, the app provides a scalable digital infrastructure for coordinating needs-targeted care from collaborating ICU teams and palliative care specialists. In pilot work, PCplanner reduced unmet needs, psychological distress, and length of stay while increasing goal concordant care, communication, and hospice utilization. While these data are promising, the intervention requires a rigorous evaluation of efficacy.¹

3. Study Design

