This is a 5-year, randomized controlled trial (RCT) that aims to test a native, novel web application called "PCplanner" developed by an external technology vendor, One Cow Standing. PCplanner directly captures EHR data to automate the identification of older adults with palliative care needs based on clinical characteristics such as dementia and declining health status. The app engages families as partners in their loved one's care by facilitating in a self-report of actual needs. Additionally, the app provides a scalable digital infrastructure for coordinating needs-targeted care from collaborating ICU teams and palliative care specialists. The project specifically intends to randomize 150 older patients aged ≥50years, their 150 self-described family members, plus their ICU clinicians to determine if the intervention can improve family-reported unmet palliative care needs compared to standard of care.

Study Aims

The project will operationalize this goal by completing three specific aims, which are described below:

- Aim 1: Optimize the usability of the PCplanner mobile app, specifically for older adults.
 Approach and goal: To optimize the PCplanner mobile app platform before Aim 2's clinical trial, key features will be added, based on user testing feedback, compatible for older adult caregivers and clinicians. Iterative revisions based on usability participant feedback will be performed until the app platform achieves 'excellent' usability (i.e., mean Systems Usability Scale (SUS) score >60).
- **Aim 2**: Test the PCplanner intervention's efficacy vs. usual care in a randomized clinical trial (RCT). *Hypotheses*: Compared to usual care at 8 days post-randomization, PCplanner-augmented care will improve family-reported unmet palliative care needs. It will also improve short-term and long-term (3-month) secondary outcomes among family caregivers

Protocol Version: 5.1 Dated: 13 June 2022 Page 6 of 42

(psychological distress symptoms, quality of communication), patients (receipt of goal concordant treatment), and health systems (length of stay). *Approach and goal:* In academic and community medical center settings, the study team will test these hypotheses among the family caregivers of medical and surgical ICU patients with dementia, declining health status, poor functioning, and other characteristics common to the aging experience.

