Randomization will be stratified by three variables:

Protocol Version: 5.1 Dated: 13 June 2022 Page 8 of 42

- Department location at the time of ICU admission and informed consent (i.e., Medical versus Surgical)
- Palliative Care Trigger type (i.e., Acute versus Chronic; see Appendix 2)
- Baseline NEST score (i.e., ≥25 vs. <25 but ≥10)

All family members, regardless of their randomization arm will be asked to complete a total of four surveys, as listed below (see Appendix 3 for survey timeline):

- T1: to be completed within 72 hours of informed consent; study day 1
- T2: to be completed on study day 4
- T3: to be completed on study day 8
- T4: to be completed on study day 90

Surveys are completed remotely and electronically via the web application by the enrolled family member. Reminders are automatically provided by the PCplanner platform to the family members via email and/or text alerts to complete the surveys (Appendix 4).

Patients enrolled into this study, at the consent of their legally authorized representative (LAR), will passively participate in the study. Passive participation includes allowing the study team to access and abstract relevant clinical data from the patient's EMR. The clinical data abstracted for the purposes of this research project will be housed in the secure, EDC (REDCap).

Clinicians, whether ICU attending or Palliative Care, will be asked to complete a baseline survey at the time in which informed consent is obtained. The baseline survey will collect relevant information from the clinician, such as sociodemographic and professional information, as well a contact information (e.g., email address and cell phone number). Clinicians, who are assigned to an intervention family, will receive automatic text and/or email alerts via the web application informing them of the completed survey(s), reported needs, and the need to complete a family meeting.

Aim 3

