At each specified time point above, the study team will abstract, as needed, relevant clinical data, as defined in the study EDC manual of procedures (MOP) and enter into the EDC, REDCap.

Compensation

Compensation for study participation will be provided to each family member via Greenphire. Participants may receive up to a total of \$60 for study completion:

- T1: \$15.00
- T2: \$15.00
- T3: \$15.00
- T4: \$15.00

Compensation for study participants in aims 1 and 3 will also be provided. Participants who partake in aim 1 or 3 will receive a one-time payment of \$15.00 for the completion of the single study visit.

6. Subject Participation Duration: For those subjects enrolled in Aims 1 and 3, we anticipate their study participation consisting of only one study survey, which will last for 30-60 minutes. For the RCT (Aim 2), it will require 3 months for participants to complete the entire study from the time of randomization, including the intervention and all the follow up surveys.

7. Enrollment sites

This study will be conducted at Duke University Health (DUH), Duke Regional Hospital (DRH), and Duke Raleigh Hospital—all sites within the Duke University Health System.

8. Statistical Design, Analyses, Sample Size and Power Statistical Design and Analyses Plan *Aim 1*

Protocol Version: 5.1 Dated: 13 June 2022 Page 14 of 42

After programming is complete, the study team will determine PCplanner usability using a 'system-user-task-environment' mixed-methods approach. The study team will interviews with healthy volunteers to determine app usability. During the single 30-minute sessions participants will complete: a 'think aloud' protocol in which CRCs record comments as PCplanner is used; a semi-structured interview, and the 10-item (0 [lowest] to 100 [highest]) industry-standard Systems Usability Scale (SUS). App revisions that address the needs of all users. The study team anticipate 2-3 cycles of 5-10 users each will achieve our testable hypothesis that PCplanner will attain a mean SUS score >60 ('excellent' usability). 33,34

Aim 2

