We will test the primary study hypothesis that the NEST score is lower (i.e., fewer unmet needs) for intervention family caregivers compared to usual care at T3 (~1-week post-randomization). All participants will be analyzed as part of the group they were assigned, regardless of adherence or crossover status (i.e., intention to treat). We will use a general linear model to estimate mean NEST changes and corresponding confidence intervals over time using SAS PROC MIXED (SAS Institute, Cary NC). Different correlation structures will be examined (e.g., unstructured, autoregressive) and model fit indices will be used to guide the choice of the final model's structure.

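### Hospital is neither a stratification factor nor a term in any planned model, which costs some precision in the NEST comparison but causes no bias

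*Combined protocol and SAP*

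**What the plan says.** Section 2 (Background) says of ICU palliative care in general: "Yet the quality of ICU-based palliative care is highly variable across clinicians and hospitals".

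The hypotheses are to be tested "In academic and community medical center settings" (section 3, Study Aims, Aim 2). Section 7 names the sites: "This study will be conducted at Duke University Health (DUH), Duke Regional Hospital (DRH), and Duke Raleigh Hospital", all within one health system.

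The Study Overview for Aim 2 says: "Randomization will be stratified by three variables". The first of these is "Department location at the time of ICU admission and informed consent (i.e., Medical versus Surgical"). The other two are whether the trigger is acute or chronic, and the NEST band at baseline (25 or more versus 10 to below 25). The first factor is defined as medical versus surgical, so it does not stand for hospital.

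Section 8, Aim 2, gives the primary analysis: "We will use a general linear model to estimate mean NEST changes and corresponding confidence intervals over time". It lists no covariates. The PHQ-9, GAD-7 and PTSS analyses follow the same pattern. The goal-concordance logistic model adjusts for the stratification variables, which exclude hospital. The length-of-stay (LOS) analyses are a proportional hazards model, a chi-square test and a rank test, none with a hospital term.

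Hospital is nevertheless available: the enrolment log in section 5 records where each patient was enrolled. Section 12 has the DSMB look at site performance, but not as part of the efficacy analysis.

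**The concern.** NEST is described as sampling the domains of palliative care quality, and the protocol says that this quality varies between hospitals. Usual care in the control arm depends on local ICU clinicians. The intervention also runs through the local ICU attending and palliative care team. The protocol's own reasoning therefore makes hospital a plausible source of variation in the primary outcome.

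If NEST change over the 8 days differs by hospital, that variation stays in the residual of the planned analysis. The standard error of the treatment contrast is then somewhat larger than it need be. What is at stake is power and the width of the confidence interval. A term prespecified now is also easier to defend than one added after the data are seen.

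**Working it through.** **1. Reproduce the plan's figure.** Inputs from section 8, Sample Size and Power: difference 8.80, SD 21.1, correlation 0.64, 65 evaluable per arm, 80% power. The 5% type I error appears in the PHQ-9 sentence; two-sided is assumed.
- SD of change = 21.1 × √(2 × (1 − 0.64)) = 17.90
- SE = 17.90 × √(2/65) = 3.14
- Power = Φ(8.80/3.14 − 1.96) = 80.0%, and the required n is 65 per arm.

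The stated sample size reproduces.

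**2. Choose a range for the hospital effect (assumed).** The documents give neither the hospital mix nor any hospital difference. Let p be the share of families from community hospitals and d the hospital difference in mean NEST change. The share of variance explained is f = p(1 − p)d²/17.90².
- p = 0.2, d = 5: 4/320.6 = 1.2%
- p = 0.4, d = 10: 24/320.6 = 7.5%

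This gives a working range of about 1-8%. For smaller gaps, p = 0.2 with d = 1 gives 0.05%, and p = 0.4 with d = 3 gives 0.7%.

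**3. Gain from effective adjustment, if SD 21.1 already contains hospital variance.** Adjusted SE = 3.14 × √(1 − f).

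| f | Adjusted SE | Power at 8.80 | SD of chance-imbalance part |
|---|---|---|---|
| 0 | 3.14 | 80.0% | 0 |
| 0.01 | 3.12 | 80.4% | 0.31 |
| 0.05 | 3.06 | 82.0% | 0.70 |
| 0.075 | 3.02 | 83.0% | 0.86 |

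For d of 1-3 units, power is 80.0-80.3%, so the gain is practically nil.

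**4. If SD 21.1 excludes hospital variance.** The unadjusted SD becomes 17.90/√(1 − f). Power of the planned analysis is then 79.6% at f = 0.01 and 78.0% at f = 0.05, and adjustment restores about 80%.

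**5. Imbalance and interval width are one quantity.** The SD of the imbalance contribution is 17.90 × √f × √(2/65). At f = 0.05, 0.70² + 3.06² = 9.85, which equals 3.14² = 9.86 up to rounding. The unadjusted SE already contains the imbalance part, so the two must not be added.

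**6. Bias and type I error.** Simulation with hospital shares 60/20/20 and a 10-unit gap gave a mean shift of about 0 and an unadjusted type I error of 5.1%.

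**7. Which hospital term helps.** In a repeated-measures model, a hospital main effect shifts every time point equally. It cancels from T3 minus T1, so the treatment-by-time contrast is unchanged. Simulated SEs (65 per arm, T1 and T3, unstructured covariance) confirm this:

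| Setting | No hospital term | Main effect only | Hospital-by-time |
|---|---|---|---|
| p = 0.4, d = 10 | 3.151 | 3.151 | 3.027 |
| p = 0.2, d = 5 | 3.178 | 3.178 | 3.170 |

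A second simulation at p = 0.4, d = 10 gave 3.097, 3.097 and 3.019. In a model with baseline NEST as a covariate, adding hospital lowered the SE from 2.80 to 2.70.

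**The case against.** The strongest case against is that the harm is small and unproven. The Background sentence describes ICU care in general. It gives no figure for these three hospitals, which share one health system, and it names clinicians as well as hospitals. Modelling change already removes stable hospital differences in baseline NEST, so only differences in change matter. The upper assumption of a 10-unit gap exceeds the 8.80-unit target effect. The sample size reproduces without a hospital term. The primary model does not name even the three stratification factors, so singling out hospital may look like preference.

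Most of this stands, and it limits the point to a minor improvement. It does not remove the point: the protocol itself raises hospital variation, the variable is already recorded, and adjustment is cheap.

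A reader might go further and infer that omitting hospital biases the treatment estimate, inflates type I error or invalidates the sample size. The documents do not support that. Families are randomised individually, and the planned interval already covers the chance imbalance. A reader might also count imbalance and a wider interval as two harms; step 5 shows that they are one.

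**Conclusion.** The point holds as a modest loss of precision. Hospital is missing from both the strata and every planned model, in a trial at three hospitals whose rationale cites variation between hospitals. There is no bias, and type I error stays near 5%.

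The size is unknown. Under the assumption that hospital explains 1-8% of the variance of NEST change, effective adjustment moves power from 80.0% to about 80.4-83%. If hospital gaps are only a few units, the gain is close to nil. These figures assume that the planning SD includes hospital variance; if it does not, the unadjusted plan falls slightly below 80% by a similar amount. The gain also depends on the form of the term, since a main effect alone in the repeated-measures model yields none.

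**What to change.** In section 8, Aim 2, prespecify hospital (three levels) in the primary NEST model in one of two forms:
- hospital-by-time terms in the repeated-measures model; or
- a hospital fixed effect in a model of post-baseline NEST with baseline NEST as a covariate.

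Use the same form for PHQ-9, GAD-7 and PTSS. Add hospital to the goal-concordance logistic model and to the LOS proportional hazards model. The chi-square test and the rank test take no covariate and stay as they are. Fix the coding of hospital before outcome data are seen, with no later choice between three levels and two.

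Leave the randomisation strata unchanged. Adding a three-level factor to the existing 2 × 2 × 2 strata would give 24 cells for 150 participants, about 6 per cell.

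The cost is a short addition to the analysis plan and no new data. It uses 2 degrees of freedom per time point, so up to 6 with NEST at T1, T2 and T3. If hospitals do not differ, the loss of precision is negligible.
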